### **Standard Burn Center Wound Treatment Regimen**

- For all groups, change dressing as directed.

- Primary dressings are variable and based on the moisture content, microorganism load and perception of infection. Wound cultures will be taken at every visit. In general, wounds respond differently to various topical treatments. Through our clinical practice, we have found that wounds plateau with the same topical for greater than 4 weeks, hence changing antimicrobial topical helps to manage the bacterial overgrowth. Dressings for both the control group and treatment group include ointment-based dressing and non-ointment-based dressings consisting of silver product. We will start with our application of our slurry, a 1:1:1 ratio of Nystatin ointment, Mupirocin Ointment, and Bacitracin Ointment. This slurry will be applied directly to the cleansed wound, followed by silver gauze and/ or foam product to all wounds. Types of silver product, site and comfort predict use of Restore, Mepilex-AG, or Mepitel-AG. If allergies to the above slurry occurs, we will use medical honey with or without bacitracin. If ointment related rashes present we will transition to silver product only or silver product plus medical honey.
- Secondary dressing: gauze and ace wrap are used to protect wound from shear and desiccation.
- If a patient is allergic to any of the above dressings, alternative dressings will be supplied per standard wound care practice in our clinic.

**Table 3. PATIENT STUDY CALENDAR:**

	Visit 1 (Screening)	Visit 2 (6 weeks +/- 1 week from last visit)	Visit 3 (6 weeks +/- 1 week from last visit)	Visit 4 (6 weeks +/- 1 week from last visit)	Visit 5 (3 months +/- 1 week from last visit)
Informed Consent	X				
Eligibility	X				
Medical History	X				
Vitals (VAS, HR, BP, RR, O2 Sat, Weight, Height)	X	X	X	X	X
Randomization		X			
Physical Exam	X	X	X	X	X
Pregnancy Test	X 				
Injection of pAF (1ml/5cm  )- Treatment group		X	X		
Burn Center SOC	X	X	X	X	X
Manual Measurement	X	X	X	X	X
Pain Assessment	X	X	X	X	X
Laboratory Tests	X			X	
Wound Culture Swabs	X	X	X	X	X
Digital Image	X	X	X	X	X
Adverse Events Noted		X	X	X	X
Wound assessment	X	X	X	X	X

Follow-up phone call to assess adverse events		X 	X 		
---	--	----------------	----------------	--	--

Only applicable to women of childbearing potential

Follow-up phone call within 24 hours AND 5-7 days after visit to assess adverse events and medications.

Applicable study procedures may be completed via telehealth or by phone, at the discretion of the treating provider.

**DRUG DISPENSATION AND RANDOMIZATION:**

Upon verification at Visit 2 that the patient’s wound is still eligible the patient’s largest wound will be randomized to the pAF arm or to the standard-of-care arm, and the CTRM facility will be notified. If the wound is randomized to the pAF arm, the CTRM will package the pAF on dry ice and transport the pAF to the Burn Unit.

The amniotic fluid or investigational product (IP) comes frozen in a nunc cryovial. The frozen IP is thawed at room temperature until the last visible ice crystal is dissolved.

**6- ASSESSMENTS**

**ASSESSMENT OF RESPONSE:**

Assessment of response will be performed at every follow up visit.

**Wound assessment:**

Wound assessments will be performed over the course of 5 exams: Visit 1-screening exam, Visit 2, Visit 3, Visit 4 and Visit 5.

Wound surface area will be calculated. Additionally, maximal length, width and depth of wound will also be measured.

Digital images will be captured at each visit using our image capture software.

The digital photography will be standardized as follows: A ruler will be present in photographs taken at each study visit. Photography will proceed using an iPad camera. We will incorporate a standard background for all photographs to help standardize the iPad’s auto color balance. Photos will be taken in normal anatomical positions at a defined distance from the site of interest according to our standard operating procedure. Typically, for best wound image capture flash or direct lights are contraindicated, hence normal clinic room lighting is sufficient. .

Wound digital images will be assessed and evaluated by a University Staff member or contracted professional blinded to both the control and treatment group. Length and width may have substantial variability. Hence, ImageJ software is used to assess area of the wound after the perimeter of the wound is manually outlined (to a reasonable accuracy). It provides more objective assessment of the size of the wound, lending more validity to the wound measurements.

### ASSESSMENT OF SAFETY:

Safety and tolerability will be evaluated by the PI and/ or trained physician from the results of reported signs and symptoms and scheduled physical examinations, for every follow-up visit. AEs will also be assessed by phone within 24 hours AND 5-7 days after Visit 2 and Visit 3 (injection visits). Unresolved AEs will be monitored for 1 year. More frequent safety evaluations may be performed if clinically indicated or at the discretion of the investigator. SAEs will be reported within 24 hours of discovery to the central Data Coordinating Center.

## **7- SAFETY MONITORING**

### **Adverse Event Reporting**

The site investigator is responsible for evaluating all adverse events at their Clinical Center and ensuring that they are properly reported. Adverse events that occur during this study will be recorded. The nature of each experience, date and time (where appropriate) of onset, outcome, course, and relationship to treatment will be documented.

### Definition of Adverse Event and Serious Adverse Event

Adverse Event (AE) means any untoward medical occurrence associated with the use of an intervention in humans, whether or not considered intervention-related (21 CFR 312.32 (a)). An event constitutes a disease, a set of related signs or symptoms, or a single sign or symptom.

Serious Adverse Event (SAE): A serious adverse event (SAE) for this population is an adverse event that:

- results in death; or
- is life-threatening (the patient was, in the view of the site investigator, in immediate danger of death from the event as it occurred); or
- requires inpatient hospitalization or prolongs an existing hospitalization; or
- results in persistent or significant disability or incapacity; or
- results in congenital anomaly/birth defect; or
- is any other event that, based upon appropriate medical judgment, may jeopardize the subject's health and may require medical or surgical intervention to prevent one of the other outcomes listed in this definition.

### Classification of an Adverse Event (Relatedness, Severity, and Expectedness)

Relatedness: The suspected relationship between study interventions and any adverse event will be determined by the site investigator using the criteria below. Relatedness must be assessed by an investigator and may not be assessed by a research coordinator.

- Not Related: The event is clearly related to other factors, such as the subject's clinical state, therapeutic interventions, or concomitant drugs administered to the subject.

- Possibly Related: The event follows compatible temporal sequence from the time of beginning the assigned study intervention, but could have been produced by other factors such as the subject's clinical state, therapeutic interventions, or concomitant drugs administered to the subject.
- Probably Related: The event follows a reasonable temporal sequence from the time of beginning the assigned study intervention, and *cannot be reasonably explained* by other factors such as the subject's clinical state, therapeutic interventions, or concomitant drugs administered to the subject.

Severity: The severity, which is a measure of intensity, of clinical adverse events and laboratory abnormalities will be recorded by the site investigator and categorized. The following guidelines will be used to describe severity.

- Mild: The event requires minimal or no treatment and does not interfere with the participant's daily activities.
- Moderate: The event results in a low level of inconvenience or concern with the therapeutic measures. Moderate events may cause some interference with functioning.
- Severe: The event interrupts a participant's usual daily activity and may require systemic drug therapy or other treatment. Severe events are usually potentially life-threatening or incapacitating. Of note, the term "severe" does not necessarily equate to "serious".

***Expectedness of the Event: All adverse events, including serious adverse events, will be evaluated as to whether their occurrence was expected or unexpected. An AE will be considered unexpected if the nature, severity, or frequency of the event is not consistent with the risk information described for the study intervention. Expected adverse events for this study are:***

- ***Infection/ Cellulitis***
- ***Local bleeding***
- ***Purulent drainage***
- ***Inflammation***
- ***Rash***

Treatment or Action Taken: For each adverse event, the site investigator will record whether an intervention was required:

- Medical or surgical procedure
- Concomitant medication: started, changed, or discontinued
- Other, specify
- No action taken

Outcome of Event: Finally, the site investigator will record the clinical outcome of each adverse event as follows:

- Death
- Recovered and the patient returned to baseline status
- Recovered with permanent sequelae
- Symptoms persist

#### Time Period for Adverse Events

For purposes of this study, events that occur following participant consent through the last study visit will be reported as adverse events. Serious adverse events, unexpected medically attended events, and new onset chronic illnesses will be recorded from consent through Visit 5 (or the last available status before Visit 5 if the subject does not complete Visit 5).

#### Data Collection Procedures for Adverse Events

After patient consent, all adverse events (including serious adverse events) will be recorded according to relatedness, severity, and expectedness, as well as their duration and any treatment prescribed. Any medical condition present at the time of consent, recorded in the patient's baseline history at study entry, which remains unchanged or improves (unless the clinician feels it is clinically relevant), will not be recorded as an adverse event at subsequent evaluations. However, worsening of a medical condition that was present at the time of consent will be considered a new adverse event and reported.

Adverse events will be coded using the MedDRA coding vocabulary. Coding will be done centrally at the Data Coordinating Center as this requires specific training.

#### Unanticipated Problems (UP)

Unanticipated problems (UP) are defined as incidents, experiences, or outcomes that are unexpected, related or possibly related to participation in the study, and suggest that the research places subjects at a greater risk of harm than was previously known or recognized. The site investigator will report unanticipated problems to the Data Coordinating Center within 24 hours of becoming aware of the event. A detailed completed report will be required to be sent to the Data Coordinating Center within 3 working days of becoming aware of the event. After receipt of the complete report, the Data Coordinating Center will report these unanticipated problems to the funding Program Official or Project Officer in an expedited manner (as close to 24 hours as possible).

In accordance with local IRB requirements, the site investigator may be required to report such unanticipated problems to the IRB in addition to notifying the Data Coordinating Center. In the event that the medical monitor believes that such an event warrants emergent suspension of enrollment in the trial, and funding staff cannot be reached expeditiously, the Data Coordinating Center will notify the study investigator and all site investigators to cease enrollment in the trial.

#### **Monitoring Serious Adverse Events**

A qualified physician will be designated to fulfill the function of the medical monitor for this study. Site investigators and/or research coordinators will report serious adverse events to the Data Coordinating Center within 24 hours of becoming aware of the event. A detailed completed report will be required to be sent to the Data Coordinating Center within 3

working days of becoming aware of the event, and the medical monitor will assess all serious adverse events reported from site investigators.

For each of these serious adverse events, the site investigator will provide sufficient medical history and clinical details for a safety assessment to be made with regard to continuation of the trial. The medical monitor will sign off on each SAE report after review. All SAE reports will be retained at the Data Coordinating Center, and all SAE reports will be available for review by funding staff. The SAE reporting process may be incorporated into the Electronic Data Capture (EDC) System in use for the study.

In the unlikely event that the medical monitor believes an unexpected and study-related SAE warrants emergent cessation of enrollment in the trial, funding staff will be immediately consulted. If these individuals concur with the judgment of the medical monitor, or if the funding staff cannot be reached expeditiously, the Data Coordinating Center will notify the study investigator and all site investigators to cease enrollment in the trial. Resumption of enrollment will not occur without consent of the funding staff.

In accordance with local IRB requirements, the site investigator may be required to report such events to the IRB in addition to notifying the Data Coordinating Center.

#### **Follow-up of Serious, Unexpected and Related Adverse Events**

All serious, unexpected and related adverse events, that are unresolved at the time of the patient's termination from the study, will be followed by the site investigators until the events are resolved, subject is lost to follow-up, the adverse event is otherwise explained or has stabilized, or 12 months have passed from the time of last study dose.

#### **PATIENT WITHDRAWAL FROM STUDY:**

A subject may withdraw their consent at any time without effect to their care.

#### **DISCONTINUATION OF STUDY DRUG:**

pAF-specific treatment will be discontinued if any of the following occur:

- Discovery of new information which makes the subject ineligible to continue participation in the study. This could include systemic sepsis, disseminated infections requiring inpatient hospitalization, worsening infection of the wound, such as necrosis or surgical intervention, increase in wound size by 50% from Visit 2 measurement, development of osteomyelitis, etc.
- Severe allergic reaction possibly related to the investigational product.
- Patient receives any investigational agent/intervention to the wound outside the study visits or is non-compliant with care between Visits 2 and 3.
- Any other condition that in the opinion of the treating physician are not compatible with participation in this study.

The study PI, treating clinicians and research staff will monitor closely for the above events, as well as any additional adverse events that occur while the subject is receiving treatment. Adverse events will be reported immediately upon discovery of the event to the Data Coordinating Center and assessed for seriousness, relatedness, severity, and expectedness.

The DSMB will meet regularly to review adverse events, safety analyses and study data and will have access to the actual treatment assignments for each group.

If study drug is discontinued, we will continue to follow the patient and monitor for safety and efficacy endpoints.

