7.3 Secondary Outcome Analysis

The secondary outcome is the percentage reduction in wound area at Visit 5 relative to wound area at Visit 2. Because reduction in wound area at Visits 3 and 4 are exploratory outcomes, the general definition for deriving percent reduction in wound area at Visit k relative to Visit 2 is

$$1 - \frac{\text{Visit } k \text{ wound area}}{\text{Visit 2 wound area}} \times 100\%,$$

with all measurements expressed as the area determined through the imaging software. Wound area will be reported in (cm^2), although for purposes of the percent reduction the units are immaterial. The percent reductions will be summarized overall and by assigned treatment arm for the ITT population, using means and standard deviations or medians and interquartile ranges, as appropriate given the observed skewness and presence of extreme outliers.

The inclusion criteria limit the study to wounds which are difficult to heal, explaining why patients are not randomized if the wound area shrinks significantly between Visits 1 and 2. Therefore, any greater reduction in wound size with pAF than with SOC will suggest efficacy of pAF for wound treatment. To describe a trend in a statistical hypothesis testing framework, the following two-sided hypothesis will be assessed:

$$H_0 : \mu_{pAF} = \mu_{SOC} \text{ versus } H_1 : \mu_{pAF} \neq \mu_{SOC}.$$

Note that μ_{pAF} (μ_{SOC}) represents the average percent reduction in wound area at Visit 5 compared to Visit 2 for the pAF (SOC) treatment.

To provide an intuitive effect size, percentage change from Visit 2 will be computed at Visits 3, 4, and 5 (approximately 6, 12, and 25 weeks after randomization). If there are study visits outside of the visit's ± 1 week window, all percentages will be divided by the number of elapsed days since Visit 2, so the outcome is expressed as a percentage change per day.

If the change in wound size at Visit 5 follows a reasonably symmetric distribution within each treatment arm, then a two-sided, two-sample, unpooled t-test will be performed to compare the mean percentage reductions at Visit 5 between arms for the ITT population. If the distribution is very asymmetrical in one or both arms, a Wilcoxon rank sum test will be used. In either case, Rubin's rules will be used to combine inferences across the multiply imputed data sets and the test will be declared statistically significant if the two-sided p-value is ≤ 0.05 .

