An exploratory endpoint is whether or not the randomized wound is closed at Visit 5. Fisher's exact test will be used to test for an association between treatment arm and whether the wound is closed at Visit 5. This will be assessed for the ITT population. In the principal analysis of this outcome, only participants with a nonmissing Visit 5 wound closure status will be included. If feasible, multiple imputation will be used to fill in missing wound closure statuses, with candidate variables in the imputation model possibly including variables such as treatment arm, wound closure status at visits 3 and 4, wound area at Visit 1 per the imaging software, and percent reduction in wound area from Visit 1 to Visit 2.

7.4.4 Wound Closure Prior to Visit 5

Another exploratory endpoint is whether or not the randomized wound was closed at Visit 3 and/or Visit 4, regardless of whether it later recurred. This will be determined by having the wound area per the imaging software assessment be equal to 0. The number and percentage of wounds closed prior to Visit 5 will be summarized, overall and by treatment arm, for the ITT population.

7.4.5 Wound Recurrence at Visit 5

This exploratory endpoint is limited to those from the ITT population whose randomized wound closed prior to Visit 5. Among this subset, the number and percent whose wound was open at the time of Visit 5 will be reported overall and by treatment arm. If the denominator is not zero, the corresponding percentage will also be displayed, overall and by treatment arm.

7.4.6 Hypertrophic Scar Formation at Visit 5

This exploratory endpoint is measured by the modified Vancouver Scar Scale (mVSS) total score and is applicable to those from the ITT population whose randomized wound is closed at Visit 5. Among this subset, the mean and standard deviation (or median and interquartile range) will be summarized overall and by treatment arm for the applicable subjects with nonmissing mVSS total scores.

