8 SAMPLE SIZE DETERMINATION

A sample size of $n = 30$ patients per group (total $n = 60$) is expected, though this may differ slightly because of the randomization procedure. Thirty participants in the pAF group with no study-related serious adverse events will provide a lower bound of the 95% one-sided exact binomial confidence interval for safety of 90% and provide enough evidence to move on to the next phase of study.

The power calculation depends on several assumptions:

- That 30 subjects are assigned to each treatment arm and that the secondary outcome is observed for all 60 subjects;
- That each subject has wound closure at Visit 5 (i.e., 100% wound area reduction relative to Visit 2) with probability $p_{SOC} = 0.2$ or $p_{pAF} = 0.5$ in the SOC and pAF arms, respectively; AND
- That for the remaining subjects in each arm, the wound area reduction percentage is uniformly distributed between 0% and 100%.

Using the Wilcoxon rank sum test (in this scenario, the response is very skewed in the pAF treatment arm), the Monte Carlo estimate of power is approximately 54%.

The trial has only modest power to detect statistically significant efficacy of pAF, but this is not unexpected for a phase I/II trial. More importantly, the sample size is sufficiently large to support the safety of moving on to the next phase of study if no study-related SAEs occur in the pAF arm, and the next phase of study would be appropriately powered for assessing efficacy.

pAF_in_Wounds_SAP_v_1_0

Final Audit Report

2021-03-11

Created: 2021-03-11
By: [name] ([contact])
Status: Signed
Transaction ID: CBJCHBCAABAAvUMP3dZCaNupqQJtavUadHtUrEKt9kc0

"pAF_in_Wounds_SAP_v_1_0" History

-  Document created by [name] ([contact])
2021-03-11 - 10:42:19 PM GMT- IP address: [name]
-  Document emailed to [name] MD ([contact]) for signature
2021-03-11 - 10:43:29 PM GMT
-  Email viewed by [name] MD ([contact])
2021-03-11 - 11:51:14 PM GMT- IP address: [name]
-  Document e-signed by [name] MD ([contact])
Signature Date: 2021-03-11 - 11:51:42 PM GMT - Time Source: server- IP address: [name]
-  Agreement completed.
2021-03-11 - 11:51:42 PM GMT

Adobe Sign

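### No rule scores an index wound that is grafted, surgically closed or amputated after randomisation, and the area formula could give it 100% reduction

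*Protocol*

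**What the plan says.** **Surgery and follow-up.** Among the reasons to stop pAF, the protocol (Discontinuation of Study Drug) lists "worsening infection of the wound, such as necrosis or surgical intervention". It then states: "If study drug is discontinued, we will continue to follow the patient and monitor for safety and efficacy endpoints". SAP 3.4 asks for follow-up of every randomised subject whatever their compliance, except after death or formal withdrawal.

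**Scoring.** SAP 7.3 defines the secondary outcome as the percent reduction from Visit 2 to Visit 5, "with all measurements expressed as the area determined through the imaging software", in the ITT population. Protocol section 8 gives the same formula. Neither makes an exception for surgery.

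**Closure.** For closure before Visit 5, SAP 7.4.4 says: "This will be determined by having the wound area per the imaging software assessment be equal to 0". The recurrence analysis in 7.4.5 is restricted to wounds that closed before Visit 5. SAP 7.4.3, on closure at Visit 5, gives no criterion.

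**What is not covered.** Skin grafting appears only as an entry exclusion. Amputation and surgical closure of the index wound are not mentioned. The per-protocol population (SAP 4.2.4) removes outside investigational wound care, not conventional surgery. SAP 5.2 has separate treatments for values that are not applicable (excluded), implied (used as implied) and missing (imputed for the secondary outcome). It does not say which applies to these wounds.

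**The concern.** The endpoint is meant to measure healing under pAF or standard care. A wound that fails, is grafted or closed by a surgeon, and then shows nothing to outline on the Visit 5 photograph gets the best possible score. The surgeon's result would be credited to the assigned arm.

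The secondary endpoint is the only efficacy outcome tested outside the exploratory set, and SAP 7.3 reads any greater reduction with pAF as suggesting efficacy. With about 30 subjects per arm, a few misplaced scores matter. Closure before Visit 5 and recurrence are affected too, because an imaging area of 0 counts as closure however it was reached. If the route through SAP 5.2 is chosen late in an unblinded trial, the choice could be made with the arm of each case known.

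**Working it through.** **Inputs from the documents**
- Test: two-sided at 0.05 (SAP 7.3), Wilcoxon rank sum as used in SAP 8.
- Size: "That 30 subjects are assigned to each treatment arm and that the secondary outcome is observed for all 60 subjects".
- Closure at Visit 5: 20% with SOC, 50% with pAF. Wounds not closed: uniform between 0% and 100% reduction (SAP 8).

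**Assumption.** The number of surgical cases is not in the documents. I use 1, 2 or 3 wounds in an arm of 30, taken either from the worst results or at random from unhealed wounds.

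**Step 1: reproduce the plan's figure.** Simulating the SAP 8 model with a tie-corrected normal approximation gives 54.3% power (54.0% with continuity correction), against the stated 54%. The power figure is sound.

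**Step 2: the score.** With Visit 5 area 0, reduction = 100% × (1 − 0 / Visit 2 area) = 100%, the same as a healed wound.

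**Step 3: leverage of one wound.** The planned means are 0.5 × 100 + 0.5 × 50 = 75% for pAF and 0.2 × 100 + 0.8 × 50 = 60% for SOC, a difference of 15 points. Moving one wound of 30 from 0% to 100% shifts its arm's mean by 100 / 30 = 3.3 points. Two shift it by 6.7 points.

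**Step 4: effect on the test** (100,000 simulated trials per cell; separate runs differ by about one point). The middle three columns have no true effect, with 20% closure in both arms, and show the chance of a significant result favouring pAF. The last column uses the SAP's assumed effect.

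| Wounds scored 100% | Worst pAF wounds | Random unhealed pAF wounds | Same number of worst wounds in each arm | Power, worst SOC wounds |
|---|---|---|---|---|
| 0 | 2.5% | 2.5% | 2.5% | 54% |
| 1 | 5.9% | 3.9% | 2.6% | 41% |
| 2 | 11.6% | 5.9% | 2.5% | 29% |
| 3 | 20.2% | 8.9% | 2.6% | 19% |

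When the same wounds are scored 0%, the first column stays at or below 2.5% and the last stays at 54% to 56%.

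**Step 5: as event rates.** Under the SAP's assumed effect, with cases drawn from unhealed wounds, power when they score 100% versus 0% is:
- 10% of subjects in each arm: 56.4% versus 45.6%
- 10% in SOC only: 28.3% versus 68.0%
- 10% in pAF only: 80.7% versus 32.9%

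**Step 6: why a flat 0% is not enough.** The formula allows negative values, and the protocol foresees growth of 50% from Visit 2. Such a wound scores 100% × (1 − 1.5) = −50%. If it were then grafted and scored 0%, surgery would still raise its rank.

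**The case against.** A reader might infer that every such wound has imaging area 0, so that treatment failures are bound to count as best outcomes and the error favours pAF. The documents do not support that.

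- **Area 0 is not certain.** Area comes from a person outlining the wound on an image. A graft that has not taken can still be outlined. An amputated site could be excluded, imputed or set to an implied 0 under SAP 5.2. Surgery for infection or necrosis may also leave an open wound with positive area.
- **Visit 5 closure is open.** The area-0 rule belongs to SAP 7.4.4, closure before Visit 5. SAP 7.4.3 does not say whether surgical closure counts.
- **The direction is not fixed.** If pAF works, failures would be expected more often under SOC, and the error would then hide a benefit.
- **There is a partial limit.** Under Discontinuation of Study, two pAF wounds needing emergent surgery stop the trial. The 2- and 3-wound pAF cases therefore apply only where at most one operation is emergent.
- **Harm is not hidden.** Events requiring hospitalisation are SAEs, the DSMB sees data by arm, and progression to the next phase rests on safety.

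All of this stands, and it limits how strongly the point can be put. It does not close the gap. The stopping rule leaves out non-emergent procedures and all SOC surgery. SAE reporting makes a case visible without changing its efficacy score. A successfully grafted or surgically closed wound that is imaged at Visit 5 with nothing to outline still scores 100% under the formula as written.

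**Conclusion.** The point holds as a gap in the scoring rules with a possible perverse result. It does not show that failures will be scored as successes. The formula, the ITT analysis and continued efficacy follow-up together allow a surgically covered wound to tie with true healing, and nothing in either document prevents it.

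The size depends on event counts that the documents do not give. If the cases fall in pAF only, one worst wound more than doubles the false-positive chance in favour of pAF (2.5% to about 6%), and three raise it to about 20%. For random unhealed wounds the figures are about 4% to 9%. If they fall in SOC only, one to three worst wounds cut power from 54% to between about 41% and 19%. Equal counts in both arms do not inflate false positives. These results rest on the SAP's own outcome model, complete data and the Wilcoxon test. The stated 54% power is correct, and the primary safety analysis is unaffected. The rule should be settled before the analysis.

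**What to change.** In SAP 7.3 and 7.4.1 to 7.4.5:
- Treat an index wound that is grafted, surgically closed or amputated after randomisation as a non-response from the procedure date. Score it at the lower of 0% and its last percent reduction before the procedure, so that surgery cannot improve the score of a wound that had grown. The −50% wound in Step 6 stays at −50%.
- Count it as not closed in 7.4.3 and 7.4.4.
- Leave it out of the recurrence denominator in 7.4.5 unless it had first closed without surgery.
- Report the as-measured area as a sensitivity analysis, and list the cases by arm with procedure and date.

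**Cost.** This is one scoring rule, with no change to patient care. A data field for the date and type of any index-wound procedure may be needed, because the protocol records procedures as an action taken for an adverse event, and an elective graft need not be one. The downside is that a wound healing well before an unrelated operation is scored conservatively. The sensitivity analysis and the listing would show this.
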